3.3. Study Treatment

The trial interventions will consist of a single subcutaneous (sc) immunization of PROSTVAC V or placebo in Week 1, followed by six PROSTVAC F or placebo immunizations administered in Weeks 3, 5, 9, 13, 17, and 21. Each immunization will be accompanied by administration of sc GM-CSF or placebo on the day of immunization and for the subsequent three days (sc injection within 5 mm of the original PROSTVAC VF or placebo injection site). The Treatment phase of this trial lasts for five months and is followed by an End-of-Treatment (Week 25)/Early Termination visit. During the Treatment phase, subjects will continue to be treated with vaccination therapy through PSA and/or radiological progression.

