4.1.3. Effect Size for Survival

The hazard ratio in the specific alternative hypotheses used to compute trial size is 0.68, that is, a 32% smaller hazard rate in Arm VG or Arm V as compared to Arm P. This hazard ratio is based on hazard ratio estimates from the previously completed randomized phase 2 trial with an allowance that the phase 2 trial likely provides an over-optimistic estimate of the true hazard ratio. The hazard ratio estimate from the phase 2 trial was 0.56 when delayed effect is not taken into account, and was approximately 0.5 when delayed effect is taken into account (depending on the quantification of the delayed effect – see next paragraph).

Proportional hazards regression with time-dependent covariate implementation of delayed effect was used to obtain estimates of the ultimate hazard ratio following delayed effect in the previously completed randomized phase 2 study. It was found that estimates of this ultimate hazard ratio were reasonably uniform over a range of delayed effect specifications and that having delayed effect in the model resulted in a better fit to the survival data than models without delayed effect. The delayed effect estimate of the hazard ratio is approximately 0.5. The shape of the delay of effect used to plan this trial is based on that observed in the phase 2 study, but with an allowance that the phase 2 trial likely provides an over-optimistic estimate of the true hazard ratio.

The delay of effect used in the simulations done to plan this trial is based on that observed in the randomized phase 2 study. This delay of effect is characterized as follows: the hazard ratio is initially unity (no effect) for four months, and over the next four months transitions linearly to the hypothesized 0.68.

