4.1.5. Number of Subjects and Required Number of Deaths

The number of subjects per arm is set to be 400 (Approximately 1200 total subjects). The accrual rate distribution is 19 months of linear ramp up followed by 11 months of constant rate of accrual (2.5 years to accrue approximately 1200 subjects). Note: The accrual distribution assumptions have been updated from the assumptions used originally to plan this trial and are based on current accrual experience. The table below has been revised to reflect these new accrual assumptions and there is no material modification to power, hypothesized hazard ratio, or any other important aspect of the trial design. As expected, the revised computations do change the projections for time to analysis. The assumptions used in [Table 1](#) match the assumptions used in the interim analysis planning computations outlined on pages 23 and 24. Please see [Appendix B](#) for more detail around the 19 month linear ramp followed by 11 months constant rate of accrual.

The trial is planned as an event driven trial. Simulation is used to compute the required number of deaths after setting other specifications. [Appendix A](#) to this document describes the simulation methodology. [Table 1](#) below shows the results of the simulations.

Table 1: Simulation Results

Case #	Delayed Effect	Specified # deaths	Time to specified deaths (y)	1-sided type I error probability estimate (%)	Power estimate (%)	Critical hazard ratio
1	No	340	3.4	1.17	90.2	0.784
2	Yes	340	3.3	1.13	44.5	0.784
3	Yes	534	5.1	1.23	86.1	0.823
4	No	534	5.2	1.12	98.8	0.823

Notes:

- Simulations are for the comparison of one of the experimental arms to control arm, that is, 800 subjects, 400 per arm, accrued over two years, with a 19 month ramp time followed by a constant accrual rate for 11 months (2.5 year total accrual).
- 10,000 replications for each case.
- Significance level is one-sided 0.0125. The column “One-sided type I error probability estimate (%)” from the simulations should be approximately 1.25%. Target power with delayed effect is 85% or more.
- The control arm data are generated under the exponential distribution with 22 month median survival.
- The experimental arm data under the specific alternative and when delayed effect (if applicable) are generated so that hazard rates are equal for 4 months (hazard ratio = 1), followed by a linear transition over next 4 months to target hazard ratio of 0.68, with hazard ratio = 0.68 from 8 months onward.

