7.2. Study Product Exposure

Study product exposure will be summarized by treatment arm and overall for the FAS.

Number of PROSTVAC or placebo PROSTVAC injections administered, number of GM-CSF or placebo GM-CSF injections administered and duration of treatment in days will be summarized using standard descriptive statistics. The number of subjects receiving each scheduled dose will also be summarized using frequency counts and percentages.

Duration of treatment will be calculated as date of last dose – date of first dose + 1.

Dosing details will be presented in listings for all subjects

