8.2.4. Other Analyses of Survival

The following other analyses, supporting, sensitivity, or exploratory, will be performed:

- Deaths that occur after the cutoff will not be censored.
- Clinical site homogeneity will be assessed by including in the model site grouping multi-level main effect terms and also interaction terms for arm by categorical site grouping.
- The analysis will be re-run with arm by stratum interaction added to the model statement in order to assess arm by stratum interaction. If the 2-sided P value for this multiple degree-of-freedom test of homogeneity is significant at two-sided 0.10, then the stratum-specific hazard ratio estimates and confidence intervals will be computed. If the statistical criterion is not met then the test of homogeneity will be regarded as an exploratory analysis of the data collected. Thus, the outcome of the strata homogeneity test will not affect the interpretation of significance for the primary test, but will affect the way the results are presented or subsequently analyzed.
- Effect modifier analyses will be performed for putatively prognostic factors, including those explored previously in the literature as well as those hypothesized to be predictive in the context of this study. Effect modification will be assessed one factor at a time in stratified models. Each factor will be analyzed as either a natural dichotomy, a dichotomized ordered categorical with cutpoint chosen based on biologic considerations, or a continuous variable dichotomized at the overall median. A separate effect size estimate for arm and its 95% confidence interval will be computed for each level of the dichotomy using contrast statements in SAS.
- The four Kaplan-Meier estimates (arm by factor) for each of the factors analyzed as effect modifiers will be plotted on one graph.
- Regression models with multiple added prognostic covariates will be estimated. The covariates to be added will include those explored previously in the literature as well as those hypothesized to be predictive in the context of this study. Interactions will also be explored for contribution to the model.
- Subjects randomized and not initiating study intervention will be added to the FAS and the primary analyses repeated.

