- An analysis of the relationship between dose intensity and outcome by arm will be performed. The main method will be a time-dependent covariate that increases by one for each injection. The interaction between arm and this time-dependent covariate will be the focus of this analysis.

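### If the planned delay in effect is real, the dose-intensity analysis (arm by running injection count, SAP 8.2.4) is biased toward an apparent benefit per injection

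*SAP*

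**What the plan says.** SAP 8.2.4 introduces its list of further survival analyses with "The following other analyses, supporting, sensitivity, or exploratory, will be performed". The last item concerns dose intensity and outcome by arm. Its method is given in two sentences: "The main method will be a time-dependent covariate that increases by one for each injection" and "The interaction between arm and this time-dependent covariate will be the focus of this analysis". The item has no arm-by-time term, delay term, landmark or significance level.

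SAP 3.3 sets one vaccination in Week 1, "followed by six PROSTVAC F or placebo immunizations administered in Weeks 3, 5, 9, 13, 17, and 21". The weeks are the same in every arm. SAP 4.1.3 plans the trial on a delay: "the hazard ratio is initially unity (no effect) for four months, and over the next four months transitions linearly to the hypothesized 0.68".

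The SAP separates out the delay in other places. Section 4.1.3 reports a phase 2 regression with a time-dependent delay term, and Appendix A describes a futility test that gives no weight to deaths before a pre-specified time of full or nearly full effect. Neither device is carried into the dose-intensity item.

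**The concern.** The low values of the count occur in the months when the plan expects no effect, and the top value covers almost all of the period in which the effect appears. An interaction between arm and count can then reflect early versus late follow-up rather than few versus many injections. Full adherence shows this most clearly. Every man alive at a given time has the same count, so the data hold no information on dose, yet the model still returns an estimate per injection. At stake is the interpretation of the only analysis the SAP specifies that relates doses received to survival; SAP 7.2 only describes exposure.

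**Working it through.** **Inputs.** From the SAP: 400 men per arm in each comparison; control survival as in 4.1.5 ("The control arm data are generated under the exponential distribution with 22 month median survival"); hazard ratio 1 to month 4, linear to 0.68 at month 8 (4.1.3); 19 months of ramped accrual plus 11 months constant; analysis at 534 deaths; vaccinations in Weeks 1, 3, 5, 9, 13, 17 and 21. Assumed, because the documents give no figures: the share of men who stop vaccination early (0% to 40%), and that stopping is unrelated to prognosis. The simulations are unstratified and take first dose as randomization.

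**1. Reproducing SAP Table 1** (5,000 replicates, one-sided logrank at 0.0125):

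| Case | SAP power | Reproduced |
|---|---|---|
| 1: no delay, 340 deaths | 90.2% | 90.4% |
| 2: delay, 340 deaths | 44.5% | 43.9% |
| 3: delay, 534 deaths | 86.1% (5.1 years) | 84.9% (5.05 years) |
| 4: no delay, 534 deaths | 98.8% (5.2 years) | 98.2% (5.17 years) |

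**2. Timing.** Days since first dose divided by 30.44 place the seven vaccinations at 0, 0.46, 0.92, 1.84, 2.76, 3.68 and 4.60 months. The planned hazard ratio is 1.00 at the first six. At the seventh it is 1 − 0.32 × 0.60/4 = 0.952. The part of the fall still to come is (0.952 − 0.68)/0.32 = 85%, and all of it happens with the count fixed at 7. With 28-day months the seventh vaccination is at month 5, where the planned hazard ratio is 0.92; the picture is the same.

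**3. Algebra.** With A for arm and N(t) for the count, the model is λ(t) = λ0(t) exp{b1·A + b2·N(t) + b3·A·N(t)}. For men on schedule N(t) = n(t), the same for everyone at risk at t. The factor exp{b2·n(t)} cancels from the partial likelihood, leaving log HR(t) = b1 + b3·n(t). So b3 is the slope of an arm-by-time term. A hazard ratio near 1 while n(t) is below 7 and near 0.7 once n(t) = 7 pushes b3 below zero.

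**4. Full adherence, no dose effect** (4,000 simulated trials per scenario):

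| Truth | Mean HR per injection | Significant at 0.05, two-sided | At 0.10 |
|---|---|---|---|
| Planned delay | 0.916 | 30.4% | 43.0% |
| HR 0.68 throughout | 1.000 | 5.1% | 10.3% |
| No vaccine effect | 1.000 | 5.1% | 9.9% |

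Under the delay, the fitted arm hazard ratio is 1.20 at count 1 and 0.71 at count 7, with about 108 of the 534 deaths at counts below 7. A hand check agrees: ln(0.710/1.201)/6 = −0.0876, so the hazard ratio is 0.916 per injection. With standard error 0.0604 the mean z is −1.45, and Φ(−1.96 + 1.45) ≈ 0.305, against 30.4% simulated. The estimate falls on the favourable side in 93% of trials. A separate set of 3,000 trials gave 0.918 and 28.9%.

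**5. Early stopping at random (assumed), planned delay, no dose effect** (1,000 trials each):

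| Stop early | HR per injection | Significant at 0.05 |
|---|---|---|
| 5% | 0.933 | 25.6% |
| 10% | 0.946 | 22.6% |
| 20% | 0.959 | 15.3% |
| 30% | 0.969 | 13.4% |
| 40% | 0.976 | 9.6% |

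With no delay, the same stopping rates give 4.2% to 5.7%. A second stopping pattern (a uniformly random last dose, 400 trials each, Monte Carlo error about 2 points) gave 27.5%, 18% and 11% at 5%, 15% and 30% stopping.

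**6. Allowing for the delay.** Using missed vaccinations with separate early and late arm terms, the arm-by-missed interaction is significant in 4% to 5% of trials and averages about zero. Keeping the running count and adding arm × ramp also restores the error rate: HR 1.002 and 4.5% with full adherence, 4.6% to 5.7% with 5% to 40% stopping. The standard error then rises from 0.060 to 0.102 under full adherence.

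**The case against.** The main defence is that little hangs on this analysis. It belongs to a supporting or exploratory list and has no significance level or decision rule, unlike the HLA-A2 interaction in SAP 8.5.1. The primary test, its alpha and the definition of trial success do not use it. All of that stands and limits the consequence, but an exploratory label does not remove a bias of known direction.

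A second defence is that SAP section 12 says a delay cannot be taken as certain. That is correct, and with no delay the interaction behaves properly. It argues for a model that allows a delay without imposing one.

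Third, SAP 8.2.4 names a main method, which leaves room for others. None is specified.

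Some stronger readings are tempting but are not supported:

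- *That a delay will always show up as a dose response.* By these figures the interaction is not significant in roughly 70% to 90% of trials. The uniformly favourable direction applies, almost without exception, to the significant results; across all trials the sign is favourable in 93% with full adherence and 75% with 40% stopping.
- *That the whole course precedes any effect.* The seventh vaccination falls 0.6 month into the ramp, and the count is already 7 while the planned hazard ratio is still falling.
- *That the result would be used to justify completing or extending the seven-dose schedule.* Nothing in the documents links the analysis to such a decision.
- *That the count might run to 35 (7 vaccine plus 28 GM-CSF).* SAP 7.2 lists "number of GM-CSF or placebo GM-CSF injections administered" separately from the vaccine tally, and SAP 9.1.1 classes injections as primary or booster, so 7 is the natural reading. Counting all 35 would rescale the estimate (0.983 per injection) and leave the confounding as it is (28.6% significant).

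**Conclusion.** The point holds as a bias. If the trial's own planning assumption is right, the specified interaction drifts toward a benefit per injection that the data do not contain: a hazard ratio of about 0.92 with full adherence and 0.93 to 0.97 with 5% to 30% early stopping. The chance of a nominally significant result at two-sided 0.05 is about 30% and 11% to 28% respectively, against about 5% when there is no delay or no vaccine effect.

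These sizes rest on the planned delay shape, assumed stopping rates, random stopping, an unstratified model and a borrowed significance level. Random stopping is the least realistic of these. Protocol 5.4.1 has men with pain progression or a PSA doubling time under one month counselled about other treatment, and ends vaccination for those who start it. Prognostic stopping would be a further source of bias, which was not simulated. The conclusion does not extend to the primary survival comparison.

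**What to change.** In SAP 8.2.4, replace the running count with M(t), the vaccinations missed by time t: scheduled minus received vaccine or vaccine-placebo injections. With ramp r(t) = 0 before month 4, (t − 4)/4 to month 8 and 1 afterwards, fit a stratified proportional hazards model with terms A·(1 − r), A·r, M and A·M, and test A·M. Both arm terms are needed. Together they let the early and late effects differ, and they reduce to a single effect if there is no delay; one arm term tied to the ramp would force a delay that the SAP does not regard as certain.

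This is preferable to adding a ramp term beside the running count, because for men on schedule arm × count remains an arm-by-time term, protected only if the ramp has the right shape. M(t) is zero for those men, so the comparison rests on men who missed doses. Delay shapes other than the planned one were not simulated.

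State that the result is descriptive because stopping vaccination can be prognostic, and cite Protocol 5.4.1.

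The change costs a few lines of SAP text and code. The price is wider intervals, since only men who miss doses carry dose information, and no estimate at all if nobody does.

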8.3. Secondary Endpoint (Alive Without Event [AWE] at Six Months)

The testing of AWE will have meaning in the context of type I error probability control only if the corresponding primary survival comparison meets its formal statistical criterion. The formal significance levels used for survival analysis will be used for AWE.

AWE has less statistical sensitivity than an analysis based on the closely related and traditional time-to-progression because the timing of events is ignored. Thus, AWE is inherently conservative. This trade-off is acceptable because the trial size provides adequate sensitivity for meaningful differences in the AWE proportions for each comparison. The approximate statistical sensitivity of AWE can be illustrated by assuming a simple comparison of proportions between the arms being compared. Assume a significance level of one-sided 0.0125 and that the control arm proportion is 0.5. Each comparison is based on 800 subjects, 400 per arm. The probability is 90% or greater that this statistical test will be significant if the true proportion difference is 0.126 or greater and the critical difference is 0.080.

The 95% confidence interval on the odds ratio estimate will be computed as the measure of the magnitude of effect.

All analyses of AWE will be conducted on the ITT set and repeated for the FAS as a sensitivity analysis.

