9.6 Secondary Efficacy Endpoint

The secondary efficacy endpoint is a binary assessment for Alive without Event (AWE) at six months (or early termination). The event is any of the following on or before six months: radiological progression, pain progression, chemotherapy initiation, or death. Subjects without an event prior to six months will have an evaluation for event at six months. Subjects without event who are not evaluated at six months (or early termination) will be assumed to have had an event. Thus, each subject will be defined as AWE =

1 if the subject is alive and free of event at six months (or early termination) and AWE = 0 otherwise. AWE will have a realization for every subject and therefore is amendable to an intent-to-treat analysis.

The same two comparisons as done for survival will be done for AWE, using the same significance levels. For each comparison the proportions of subjects in each arm for which AWE = 1 will be compared. The probability is 90% or greater that this statistical test will be significant if the true proportion difference is 0.1375 or greater. The critical difference is 0.092 if the control arm proportion is 0.5.

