3.2.2. Secondary Endpoint

The secondary efficacy endpoint for the study is the proportion of event-free subjects (AWE) (radiographic progression, pain progression, chemotherapy initiation, or death) at six months (or early termination) compared to placebo.

Progression events will be defined as:

- Radiographic progression (per central radiology assessment)
 - Two new lesions on bone scan, new metastases on CT scans*, or an increase size of nodal lesions per RECIST 1.1.
- Pain progression**
 - Introduction of scheduled opioid narcotics for cancer-related pain control. Scheduled opioid narcotics are defined as continuous daily use lasting more than 14 days.
- Initiation of chemotherapy for prostate cancer
- Death

* For subjects with allergies to contrast agents, MRIs for abdomen and pelvis may be performed. Only in cases where MRI is unavailable may a non-contrast CT be performed.

** The start date for an event of pain progression is defined as day 1 of first opioid regimen lasting more than 14 days.

Radiographic progression will be assessed by bone scan or CT at Screening, Week 13, Week 25 (EOT), and early termination scans. For secondary endpoint analysis, Screening scans and Week 13, Week 25 (EOT), and early termination scans will be compared by central radiology review. Bone scan and CT data will be archived up to five years past the end of the trial.

The secondary efficacy endpoint is a binary assessment for AWE at six months. Subjects without an event prior to six months will have an evaluation for event at six months. Subjects without event who are not evaluated at six months will be assumed to have had an event. Thus, each subject will be defined as AWE = 1 if the subject is alive and free of event at six months and AWE = 0 otherwise. AWE will have a realization for every subject and therefore is amendable to an intent-to-treat analysis.

The analysis of AWE is less subject to ascertainment anomalies compared to the analysis of time-to-progression because the six month assessment brings all subjects to the same level of ascertainment.

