The one-sided significance criteria to be used for early detection of efficacy analyses are 0.000135, 0.00147, 0.00501, respectively, with the adjusted final analysis to use 0.01063. These significance levels were computed using SAS PROC SEQDESIGN as one-sided O'Brien-Fleming boundaries with an overall one-sided type I error probability of 0.0125. Following is the SAS code used to compute these intervals.

```
proc seqdesign boundaryscale=pvalue;  
  design  
    nstages=4  
    info=cum(0.4 0.6 0.8 1)  
    method=obf  
    alt=upper  
    stop=reject  
    alpha=0.0125  
  ;  
run;
```

The early detection of efficacy is to use the same statistical testing methodology as specified for the primary analysis. The statistical characteristics for the interim analysis event-driven time-points and significance levels are computed using simulations. The simulation methodology for delayed effect is described in [Appendix A](#). The following table shows the statistical operating characteristics of this plan based on 10,000 simulation replicates. For example, when the alternative hypothesis is true (average hazard ratio = 0.68) then at the second interim analysis is projected for 3.2 years following the start of randomization and the estimated cumulative probability of rejecting the null hypothesis is 0.1571 (with confidence interval as shown). Also shown is the largest hazard ratio found for which the null hypothesis was rejected (rej HR), showing that at this interim analysis a hazard ratio less than or equal to 0.716 will pass the criterion for early efficacy (an estimate of the critical hazard ratio). Please note that these simulations are consistent with the targeted overall one-sided type I error of 0.0125: for analysis 4 (“#” column) the proportion of trials rejected (“rejected” column) under the null hypothesis (row with “null” in the “hyp” column) is 0.0127, and is close enough to 0.0125 considering computations were done using simulation.

Statistical Operating Characteristics of the Interim Analysis Plan

Simulation estimates (cumulative, # replications = 10000):

#	events	hyp	time	test	rejected	95% CI	rej HR		
1	214	null	2.5	futile	0.0771	0.0719 to 0.0825	≥ 1.212		
				superior	0.0000	0.0000 to 0.0004	≤ 0.000		
		alt	2.5	futile	0.0054	0.0041 to 0.0070	≥ 1.216		
				superior	0.0065	0.0050 to 0.0083	≤ 0.603		
				null	3.0	futile	0.2297	0.2215 to 0.2381	≥ 1.090
						superior	0.0013	0.0007 to 0.0022	≤ 0.712

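### The plan ties the AWE test to the survival significance levels but gives two versions of them; the look-specific version would cut AWE power below the stated 90% with no error-control benefit

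*SAP*

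**What the plan says.** SAP 8.3 gives AWE formal meaning "only if the corresponding primary survival comparison meets its formal statistical criterion" and sets its level by reference: "The formal significance levels used for survival analysis will be used for AWE". Protocol 9.6 has the same rule: "The same two comparisons as done for survival will be done for AWE, using the same significance levels".

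The survival level is stated in two ways:

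- SAP 4.1.4, SAP 8.2.2 and Protocol 9.4 give one-sided 0.0125 per comparison.
- SAP 12 and Protocol 9.8 give levels by look, at 214, 321, 427 and 534 deaths. In the SAP's words: "efficacy analyses are 0.000135, 0.00147, 0.00501, respectively, with the adjusted final analysis to use 0.01063".

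SAP 8.3 then illustrates AWE sensitivity: "Assume a significance level of one-sided 0.0125 and that the control arm proportion is 0.5". It continues "Each comparison is based on 800 subjects, 400 per arm" and "The probability is 90% or greater that this statistical test will be significant if the true proportion difference is 0.126 or greater", with a critical difference of 0.080. For the same illustration Protocol 9.6 gives 0.1375 and 0.092.

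Neither document says when AWE is tested if survival succeeds at an interim look. The interim plan covers survival only.

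**The concern.** AWE is the only secondary endpoint with a formal test, and two thresholds for it can be defended from the text. Suppose survival crosses at look 2 and AWE then gives a one-sided p-value of 0.004. That passes at 0.0125 and fails at 0.00147. The choice should not be left until the data are known.

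The look-specific reading also has a perverse effect. The earlier survival succeeds, the stricter the AWE threshold becomes, so AWE loses most sensitivity where the survival benefit is strongest. The interim levels guard against repeated testing of accumulating deaths. AWE does not accumulate in that way: each man has one value, fixed at six months.

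**Working it through.** **Inputs.** From SAP 8.3: 400 per arm, control proportion 0.5, difference 0.126 (so 0.626 on vaccine), one-sided 0.0125. From SAP 12: the four look levels and the cumulative probabilities of a survival win. From SAP Appendix B: 30 months of accrual, the last 11 at 58.6 men per month.

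**Formula.** This is the simple two-proportion comparison the SAP itself uses for illustration; the planned analysis is stratified logistic regression.

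Power = Φ[(0.126 − 1/400 − z·s0)/s1], where

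- s0 = √(2 × 0.563 × 0.437/400) = 0.03507
- s1 = √((0.25 + 0.626 × 0.374)/400) = 0.03479
- 1/400 is a continuity correction.

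The critical difference c solves c = z·√(2·p̄(1 − p̄)/400), with p̄ = 0.5 + c/2.

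**Reproducing the SAP.** At 0.0125, z = 2.241. Power = Φ[(0.1235 − 0.0786)/0.03479] = Φ(1.290) = 90.2%, or 91.3% without the correction. The critical difference is 0.079 (0.0815 with the correction), against 0.080 stated. The SAP's figures therefore fit 0.0125.

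**The same formula at each level.**

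| Level applied | z | Critical difference | Power at 0.126 | Power, uncorrected |
|---|---|---|---|---|
| 0.0125 | 2.241 | 0.079 | 90.2% | 91.3% |
| Look 1: 0.000135 | 3.643 | 0.128 | 45.1% | 48.0% |
| Look 2: 0.00147 | 2.974 | 0.105 | 70.9% | 73.4% |
| Look 3: 0.00501 | 2.575 | 0.091 | 83.0% | 84.8% |
| Final: 0.01063 | 2.303 | 0.081 | 89.0% | 90.3% |

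The look-1 row assumes complete AWE data.

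**Averaging over where survival succeeds.** The chance of first crossing at each look is the difference between successive cumulative probabilities in SAP 12.

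- Delayed effect (0.0065, 0.1571, 0.5417, 0.8388): first crossings 0.0065, 0.1506, 0.3846, 0.2971. Mean AWE power given success = (0.0065 × 0.451 + 0.1506 × 0.709 + 0.3846 × 0.830 + 0.2971 × 0.890)/0.8388 = 83%. Successes before the final look: 0.5417/0.8388 = 65%.
- No delay (0.1902, 0.6745, 0.9218, 0.9854): first crossings 0.1902, 0.4843, 0.2473, 0.0636. The same sum divided by 0.9854 gives 70%. Successes before the final look: 0.9218/0.9854 = 94%.

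These averages treat AWE and survival as independent. Death is an AWE event, so some positive correlation is likely; the documents give no value. With an assumed correlation of 0.3 to 0.5 and delayed effect, a simulation gives 86–89% under the look-specific levels against 92–94% at a fixed 0.0125, a gap of about 5 to 6 points. Without delay the gap is roughly 18 points.

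**Is the stricter level needed?** Take one comparison, with survival tested at the look-specific levels and AWE tested once at 0.0125 after a survival win.

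- If the survival null is true, a false AWE claim first needs a false survival rejection, which has probability at most 0.0125.
- If the survival null is false, a false AWE claim needs an AWE p-value below 0.0125, again with probability at most 0.0125.

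The two-comparison Bonferroni split then holds the total at 0.025, whatever the correlation. Simulation agrees: per-comparison AWE error was at most about 0.0126 (0.0125 within simulation error), and family-wise error at most about 0.0235.

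**Timing.** Accrual ends at month 30, so six-month AWE is complete at about month 36 (3.0 years). SAP 12 projects look 2 at 3.0 to 3.3 years and look 1 at 2.5 to 2.6 years. Only a look-1 win would come clearly before AWE is complete.

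**The Protocol's figures.** At 400 per arm, 0.092/√(0.5/400) = 2.60, a one-sided level of about 0.0046. At 0.005 the critical difference is 0.091 (0.093 corrected) and power at 0.1375 is 91.4% (90.2% corrected). The Protocol pair fits a level near 0.005, not 0.0125.

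**The case against.** The strongest reply is that 0.0125 is the intended level. SAP 8.2.2, just before 8.3, sets the survival criterion at 0.0125; SAP 4.1.4 and Protocol 9.4 agree; and AWE is sized at 0.0125. The plural in the AWE rule may mean only one level for each of the two comparisons. The look-specific values belong to an interim plan for survival that never mentions AWE. On this reading nothing is lost. That stands as a coherent reading, but not as the only one: under the interim plan no survival look, including the final one at 0.01063, uses 0.0125.

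A reader might infer that the survival levels simply are the look-specific ones, so that an early win cuts AWE power to 45–83%. The documents do not establish that. The 45% end also needs a look-1 win, which has probability 0.0065 under the planned delay (0.1902 without delay), and it assumes AWE data that would be incomplete then.

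A reader might also infer that 29% of men would be coded as failures at look 1. Men randomised in the preceding six months number 6 × 58.6 = 352 of 1,200, and SAP 3.2.2 says: "Subjects without event who are not evaluated at six months will be assumed to have had an event". But nothing schedules an AWE test at look 1, and some of these men would already have had a true event. The 29% is an upper bound for a scenario the text leaves open.

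Finally, the look-specific rule is conservative: it cannot inflate type I error. That is correct. The complaint is lost power and an unsettled threshold.

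**Conclusion.** The concern holds in this form: the AWE level is set by reference to survival levels that the documents state in two ways, and the choice can change the AWE result. Under 0.0125 the stated 90% power stands. Under the look-specific levels, power at a 0.126 difference is about 71%, 83% and 89% after wins at looks 2, 3 and 4. Given survival success it averages about 83% with the planned delay and 70% without, if AWE and survival are independent; with delay, plausible positive correlation narrows the shortfall to about 5 to 6 points. At the final look the loss is about one point. None of this loss is needed for error control, provided AWE is tested once on complete data and survival keeps its interim boundaries. The figures rest on a simple comparison of proportions, 400 per arm and a control proportion of 0.5. The sponsor should make the change, but the trial's primary conclusion does not depend on it.

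**What to change.** In SAP 8.3 and Protocol 9.6, replace the sentence on levels with a rule of this kind: once the matching survival comparison meets its criterion at any interim or final analysis, AWE for that comparison is tested once, at one-sided 0.0125, on all randomised subjects, after every subject has passed the six-month assessment window.

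In the same edit:

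- Reconcile the final survival level in SAP 8.2.2 (0.0125) with SAP 12 (0.01063). The four look levels together already use the 0.0125 per comparison, so a final test at 0.0125 after the interim looks would exceed it.
- Reconcile the AWE figures in Protocol 9.6 (0.1375 and 0.092) with those in SAP 8.3 (0.126 and 0.080). Otherwise the Protocol would state a 0.0125 test beside numbers that fit a level near 0.005.

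The cost is a few sentences, with no extra patients or data. After a look-1 survival win the AWE result would wait about six months. Chemotherapy and opioid starts count as AWE events and could be influenced by knowledge of the arm or the survival result, so the outstanding AWE assessments should stay blinded until the test is done.
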